DNA Collection and Extraction. DNA will be extracted from blood samples collected by a member of the study staff who is also a certified phlebotomist, labeled by coded identifiers, and sent to [name] laboratory at MGH for genotyping. If a patient is interested in providing a genetics sample but is unwilling to have their blood drawn, they will have the option to provide a saliva sample. Laboratory personnel will not have access to personal identifiers. [name] laboratory has extensive experience with the collection, extraction and genotyping of DNA. The process of DNA collection through blood and saliva samples is highly acceptable to participants and, in our hands, each sample provides approximately 60 ug of genomic DNA. Given that each genotyping assay requires only 2.5 – 5 ng of DNA, this yield will be more than adequate. After DNA extraction, sample yield is determined by picogreen analysis.

Genotyping Methods: Genotyping will be performed in [name] lab at the MGH Center for Human Genetic Research. Single nucleotide polymorphism (SNP) genotyping will be performed using the Sequenom MassArray system (Tang et al., 1999; Smoller et al., 2003). Genotyping will be performed in multiplex reactions in 384-well plates. For each assay, four duplicate samples and 4 blank samples will be included. SNPs will be used for association analyses only if they meet the following quality control criteria: 1) >90% of attempted genotypes for any SNP are successful, 2) alleles are in Hardy Weinberg equilibrium, and 3) agreement between all

duplicates and no more than 1 of 4 blanks with genotypes. Genotyping of the functional promoter variant in the *GRIN2A* gene (Itokawa et al., 2003) will be performed using the Applied Biosystems 3730 DNA Analyzer and standard protocols. GeneMapper v3.5 is used to analyze the raw results from the ABI3730, however, a genotype is not considered final until two laboratory personnel have independently checked (and corrected) the GeneMapper results and both individuals are in agreement.

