Given the small number of genetic samples, we will add BDD DNA samples collected by the PI for a separate BDD treatment study of Lexapro discontinuation as well as BDD DNA samples collected by project collaborator [name] at Brown University as part of a longitudinal BDD study. Both studies obtained consent for participants to collect DNA, to store this DNA at MGH, and to conduct genetic association studies for BDD. Only subjects who specifically consented for the genetic portion of the study had blood drawn and DNA extracted; therefore, only subjects who consented for the optional genetic study will be used for the current genotyping study. All DNA tubes/samples are fully de-identified. For the samples collected at Brown, no MGH investigators have any access to subject identifiers.

In order to conduct a BDD case-control genetic association study, we have obtained ancestry and gender-matched control DNAs from the Genome Superstruct Project (GSP), (Massachusetts General Hospital, Boston; PI: [name], [name], [name]). All of these control samples were consented for genotyping in targeted and whole-genome association studies as well as for data sharing. No control subjects who did not consent to future sharing will be used in this study. Of note, we need to conduct direct genotyping of the BDD candidate genes to control for likely experimental confounds if the BDD case DNAs were genotyped and compared to control data generated on a different platform at a different site. The DNAs all exist in the MGH PNGU Core Lab, and are fully de-identified; thus, BDD study investigators have no way of knowing to whom the samples belong.

Privacy and Confidentiality

All information gathered will be kept strictly confidential. Participants will be assigned a code number, and the participants' names will not appear on any questionnaires or therapy protocols. Moreover, the data will be stored in locked file cabinets located in locked offices. Only the study personnel will have access to the data.

Participants may also choose to provide consent for the use of their samples in related research. We have included in the consent form a description of what information will be shared with any outside investigators.

6. Biostatistical Analysis

Please note: The blind may be broken after every ten subjects to conduct preliminary analyses to assess for the efficacy of D-cycloserine.

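### The SNP call-rate rule names no group, so in the add-on case-control study a SNP that fails much more often in cases than in controls could pass quality control

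*Combined protocol and SAP*

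**What the plan says.** The protocol and SAP are one document. In section 5, under Optional Genetics Component, the Genotyping Methods paragraph sets the entry rule: "SNPs will be used for association analyses only if they meet the following quality control criteria". The first two criteria read ">90% of attempted genotypes for any SNP are successful, 2) alleles are in Hardy Weinberg equilibrium"; the third concerns duplicates and blanks ("For each assay, four duplicate samples and 4 blank samples will be included"). None is split by case or control status, DNA source or specimen type. The Hardy-Weinberg criterion has no cut-off.

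The DNA has several origins. Trial participants give blood, but if they decline a blood draw "they will have the option to provide a saliva sample". To enlarge the case group, "we will add BDD DNA samples collected by the PI for a separate BDD treatment study of Lexapro discontinuation", together with samples from a longitudinal BDD study at another university. For the case-control comparison the plan uses "ancestry and gender-matched control DNAs from the Genome Superstruct Project (GSP").

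The plan recognises experimental confounding. It genotypes the candidate genes directly in cases and controls instead of borrowing control data from another platform and site, and all the DNA is held in one core laboratory. In section 6, Evaluation of Population Structure adds 100 unlinked null SNPs to look for ancestry differences.

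**The concern.** In the case-control study, DNA source coincides with case status: no control comes from a case source, and no case from the control source. A single success rate over all samples cannot show that failures are concentrated on one side. If those failures also fall more often on some genotypes than others, the allele frequency observed in cases moves away from the truth while that in controls hardly moves. The association test would then respond to a laboratory artefact.

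The other checks do not look for this. Duplicates and blanks test concordance and contamination. The null SNPs address ancestry and cannot reveal missing genotypes at a particular candidate SNP. Yield measurement after extraction concerns the quantity of DNA, not the call rate by group. At stake is the credibility of any BDD susceptibility finding, in a plan whose Background says it wants to limit spurious associations and Type I error.

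**Working it through.** The 90% threshold is a chosen rule, so there is no plan figure to reproduce. The questions are what the rule lets through and what that does to the test.

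**1. What passes.** With k controls per case, case call rate c1 and control call rate c0, the overall rate is (c1 + k·c0)/(1 + k). It exceeds 90% when c1 > 0.90(1 + k) − k·c0.

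- k = 1, 84% and 98%: (84 + 98)/2 = 91%, passes.
- k = 2, 80% and 98%: (80 + 2×98)/3 = 276/3 = 92%, passes.
- Limit with c0 = 99%: k = 1 gives 1.80 − 0.99 = 81%; k = 2 gives 2.70 − 1.98 = 72%.

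**2. How the allele frequency moves.** Take a true minor allele frequency of 0.30 (assumed), so carriers are 1 − 0.70² = 51% of people. If carriers share one failure rate f, the observed frequency is 0.30(1 − f)/(call rate).

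- Carriers fail three times as often, cases at 84%: the non-carrier rate is 0.16/(0.49 + 3×0.51) = 0.079, so f = 0.238. Observed: 0.30×0.762/0.84 = 0.272.
- Same pattern, controls at 98%: 0.02/2.02 = 0.0099, so f = 0.030. Observed: 0.30×0.970/0.98 = 0.297.
- Only carriers fail, cases at 84%: f = 0.16/0.51 = 0.314. Observed: 0.30×0.686/0.84 = 0.245.
- Failure unrelated to genotype: 0.30 in both groups, no shift.

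**3. False-positive rates.** These come from simulation with no true association, 20,000 SNPs per scenario and a two-sided trend test at .05. The documents give no case or control numbers, and no test or level for this comparison. Assumed: 100-150 cases, minor allele frequency 0.2-0.4, and the same kind of genotype dependence in both groups, each at its own failure rate. Rates are among SNPs that pass the overall rule.

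| Failure pattern | 1:1, 84% v 98% | 1:2, 80% v 98% |
|---|---|---|
| Random | about 5% | about 5% |
| Carriers fail three times as often | 7-12% | 10-21% |
| Only carriers fail (worst case) | 12-47% | not used in the conclusion |

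At 1:1, about 65-72% of such SNPs pass the overall rule, but only 1-3% pass 90% required in each group. An overall Hardy-Weinberg filter at p > .05 leaves the false-positive rates essentially unchanged.

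**4. Sensitivity.** With 50-200 cases, frequency 0.30, controls at 99% and cases at 84% (1:1) or 78% (1:2), three-fold carrier failure gives 7-12% and 10-26%. Heterozygotes failing twice as often gives 5.5-9%. Smaller gaps matter less: with 150 per group and frequency 0.30, 90% versus 98% gives about 6.5% (three-fold) and 10% (carriers only); 94% versus 98% gives 5-6%.

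**The case against.** The strongest reply is that nothing in the documents points to a call-rate gap of 14 to 18 points. Each sample yields about 60 ug of DNA against 2.5-5 ng per assay. Saliva is an exception within one of three case sources, and the added BDD subjects gave blood. All DNA is in one laboratory and is genotyped directly. The 84% and 80% figures are illustrations chosen because they pass. Harm also needs failure that depends on genotype, since a gap alone gives 5%. The top figure of 47% requires 150 cases, frequency 0.2 and every failure in a carrier. Carriers are then 1 − 0.8² = 36% of cases, so 0.16/0.36 = 44% of them fail and nobody else does.

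All of this stands, and it limits the weight of the point. It does not close the gap. Common genotyping removes platform and site differences, but not differences in specimen, collection, extraction or storage that arise earlier.

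A reader might infer three stronger things that the text does not support. First, the plan does not state a pooled rate; it names no group, and one overall rate is the plain reading. Second, it does not follow that an artefact would be reported as a susceptibility variant, only that it could be. Third, moving the Hardy-Weinberg test to controls is not a remedy. With the artefact in cases, such a filter at .05 kept about 95% of affected SNPs, which is what it keeps when nothing is wrong, and the false-positive rate did not change.

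**Conclusion.** The point holds as a cheap improvement to the quality rule, not as evidence that the results will be wrong. As written, the rule could admit a SNP that fails in close to 20% of cases at 1:1, or close to 30% at two controls per case, provided controls succeed almost always. False positives then rise only if failure also depends on genotype: to about 7-12% at 1:1 and 10-21% at 1:2 under three-fold carrier failure, with 12-47% at 1:1 as a worst case. These figures rest on assumed sample sizes, allele frequencies, call rates, test and level, and are conditional on such a SNP existing.

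The reach is narrow. A reader might infer that the genetic predictors of treatment response, or the trial result, are compromised. They are not: the outcome and gene-by-treatment analyses in section 6 do not use the separately sourced controls, and the DCS-placebo comparison uses no genotypes. Only the add-on case-control study is concerned.

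**What to change.** For the case-control analysis, reword the first quality criterion under Genotyping Methods to require more than 90% successful genotypes separately in cases and in controls. Report the call rate for each DNA source: this trial (blood and saliva apart), the two added BDD studies and the control project. Drop or flag any SNP whose call rate differs between cases and controls, naming the test and its cut-off in advance. Do not rely on a controls-only Hardy-Weinberg test for this purpose.

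The cost is a change of wording and a few lines of code on data already produced, with no extra assays. The downside is that a few SNPs may be dropped. A per-group 90% rule will not catch small gaps: at 94% versus 98% about 96% of SNPs still pass it. The call-rate comparison is there to look for such gaps, and the inflation at that size is slight.

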In addition to those reviewed above, a larger number of proteins have been implicated in fear conditioning and extinction, including components of the MAPK and PI-3 kinase intracellular signaling cascades (Lin et al., 2003), the dopamine D1 receptor (Pickel et al., 2006), calcineurin (Lin et al., 2003), gephyrin (Chhatwal et al., 2005), AMPA glutamatergic receptors (Barad, 2005), and GABA(A) receptors (Davis & Myers, 2002). However, for this initial study of genetic influences on extinction learning and DCS augmentation, we believe it is prudent to limit multiple testing and Type I error by pursuing a focused analyses of a core set of extinction-related genes. Thus, we will examine key NMDA receptor-related genes (*GRIN1*, *GRIN2A*, *GRIN2B*, *DAAO*, *DAOA*) and extinction-related neuropeptides (*BDNF*, *NTRK2*, *CNR1*). Future studies in larger samples may permit analysis of a wider net of potentially relevant genes.

2. Specific Aims

Primary Aim:

The purpose of the proposed study is to conduct a double-blind, placebo-controlled trial of DCS augmentation of ERP in patients with BDD. Specifically, we intend to treat 50 BDD patients who will receive either DCS (100mg, n=25) or placebo (n=25) one hour before 8 of 10 behavior therapy sessions. We anticipate that some participants who sign consent for the study will be deemed ineligible after the initial screening visit. Consequently, our enrollment goal is 80 in order to reach our goal of 50 individuals who begin treatment.

We hypothesize that patients receiving DCS will show significantly more improvement in BDD symptoms, compared to patients receiving placebo. We intend to conduct the proposed study to collect sufficient pilot data to apply for an externally funded larger-scale research project.

Secondary Aim:

This treatment study also provides us with the opportunity to further explore the molecular genetics of BDD, as well as the genetic predictors of response to an extinction-based treatment. We will take a hypothesis-driven approach by focusing on genes and systems previously shown to mediate fear acquisition and NMDA-dependent extinction learning including NMDA-related glutamatergic loci (*GRIN1*, *GRIN2A*, *GRIN2B*, *DAAO*, *DAOA*) and three other genes strongly implicated in fear extinction (*BDNF*, *NTRK2*, *CNR1*). Other loci of interest in the molecular genetics of BDD include: the serotonin transporter gene, dopamine, GABA-A, and cytochrome P450 genes

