At the initial visit, we will first obtain informed consent from the participant. We will also have participants sign their initials and date if they consent to sharing their de-identified data with other researchers in our group or across studies for research purposes only. This procedure will save subjects time if they participate in more than one study at our clinic because it will eliminate repeating assessments shared between studies. The participant will then undergo a structured clinical interview and fill out several questionnaires assessing BDD symptoms, anxiety, and depression. If the participant is eligible for participation based on this evaluation, the study physician will then meet with him or her to conduct the medical evaluation (more detail below). If the participant remains eligible for the study after the medical evaluation then he or she will be randomized to receive either the D-cycloserine or placebo. The MGH research pharmacy will create and maintain the coded randomization schedule for this double-blind design and prepare and dispense the study medication (DCS or placebo) to study staff. None of the investigators will be privy to the code, except for the study physician in case of an emergency. Participants who choose to participate in the optional genetics component of the study will also have their blood drawn at this visit. In all, the initial visit will last approximately 3-4 hours. After randomization, the participant will come to the clinic for a psychoeducation/treatment planning session approximately one week later (see below for more detail). If we are unable to schedule the treatment planning session within 21 days of the screening visit, participants will be asked to complete a modified screening session directly prior to the treatment planning session. This visit will take approximately 30 minutes. This visit will last approximately 1.5 to 2 hours. The participant will not take the study medication/placebo prior to this visit. After this treatment planning session the participant will be scheduled for 10 once weekly behavior therapy sessions over a 10 week period. The first two therapy sessions will involve primarily cognitive interventions and so the study medication will not be administered prior to these sessions. The participant will be asked to come to the clinic one hour before sessions 3-10 to take the study medication/placebo in the presence of the therapist. Study medication will be kept at the clinic for the duration of the study. In addition to the therapy visits, comprehensive assessments of BDD symptoms, mood state and cognitions to assess the outcome of therapy will be given at midtreatment (after session #5), post treatment and at 1- and 6- month follow-ups. These assessments will take approximately 1 hour. BDD symptoms, CGI-I score, and depressive symptoms will be assessed via self-report questionnaires at every treatment session. These questionnaires

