
will take approximately 5 minutes to complete. A detailed assessment schedule is submitted for review.

Psychological Assessments

Comprehensive assessments of BDD symptoms, mood state and cognitions to assess the outcome of therapy will be given at pretreatment, midtreatment, post treatment and at 1- and 6- month follow-up. BDD symptoms, CGI-I score, and depressive symptoms will be assessed every treatment session.

The following instruments will be used and are submitted for review:

(1) Demographic information sheet. This sheet assesses general information such as age, years of education, etc.

(2) Structured Clinical Interview for DSM-IV (SCID; First, Spitzer, Gibbon et al., 1995). This instrument will be used to determine the Axis I psychiatric diagnosis(es).

(3) Structured Clinical Interview for DSM-IV Axis II Personality Disorders (SCID-II; First et al., 1997). Patients will complete the SCID-II self-report questionnaire; for any personality disorder for which the patient's report approaches criterion (number of criteria required minus 1), the rater will administer all interview questions for that personality disorder.

(4) Yale Brown Obsessive Compulsive Scale modified for BDD (BDD-YBOCS). This reliable and valid 12-item semi-structured clinician-administered scale, which was adapted from the Y-BOCS (Goodman et al., 1989), rates current severity of BDD symptoms (Phillips et al., 1997). It will be the study's primary outcome measure. The BDD-YBOCS has excellent interrater and test-retest reliability (ICC for total score=.99 and .88, respectively), internal consistency (Cronbach's alpha=.80), convergent validity ($r=.55$ with the CGI), and sensitivity to change with treatment (Phillips et al., 1997).

(5) BDD-Symptom Scale (BDD-SS) The PI developed the BDD-SS to rate the severity of specific BDD symptoms.

(6) Clinical Global Impression Scale (CGI) This global rating scale, which ranges from 1 (very much improved) to 7 (very much worse) on levels of improvement (CGI-I) and from 1 (normal, not at all ill) to 7 (extremely ill) on severity (CGI-S), is commonly used in pharmacotherapy trials (Guy, 1976). The CGI will be a secondary outcome measure and will also be used to determine clinical deterioration of BDD.

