Primary analyses: Our primary hypothesis is that ERP in combination with DCS is more effective than ERP in combination with a placebo. To measure this, the BDD-YBOCS will be the primary outcome measure. The main analyses will compare the two patient groups at mid-treatment and post-treatment using analysis of variance (ANOVA) and analysis of covariance (ANCOVA, controlling for BDD-YBOCS-pretreatment scores). To further determine the clinical significance of these findings, we will use the Jacobson and Truax (1991) formula to calculate the percentage of patients who fulfill the criteria for reliable and clinically significant change in each treatment condition at mid-treatment and post-treatment. Fisher's exact test for differences in frequencies of responders between the two patient groups will be performed. We will further compare the two groups at the 1- and 6-month follow-up assessments.

Power analysis: A power analysis with a sample size of 25 per group and $p < .05$ reveals that this study will convey 80% power to detect a group difference in post-treatment BDD-YBOCS scores of $d = 0.78$, which is a large effect size. Moreover, we will estimate between-group effect sizes of this pilot study to be used in designing future studies.

Secondary analyses: We hypothesize that patients who receive DCS augmentation will have greater improvement on the CGI-I, BDI, BDD-SS, and Disability Inventory at mid-treatment, post-treatment and 1- and 6-month follow-up assessments than patients who receive the placebo. ANCOVAs (controlling for pretreatment scores) and multivariate ANCOVAs (MANCOVAs) will be used for these analyses as described above, and effect sizes will be computed. Furthermore, the Cognitive and Behavioral Change Measures will be used to identify in more detail within which session, or between which sessions, any changes occurred.

Predictors of outcome: We also wish to evaluate whether ERP in combination with DCS is particularly effective or ineffective for different symptoms (as measured by the BDD Symptom Scale), attitudes (i.e., patient's judgments about the credibility of the treatment, as measured by the Expectancy Rating), or comorbid problems (e.g., depression). These factors will be included in regression analyses. We also intend to explore the relationship between minority status and treatment outcome; however, power will be limited given the small sample size.

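### Optional unblinded efficacy looks after every ten subjects contradict the blinding rule and have no error control; if interim significance counts, type I error rises from 5% to about 7–15%

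*Combined protocol and SAP*

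**What the plan says.** Section 6 (Biostatistical Analysis) begins with a note: "The blind may be broken after every ten subjects to conduct preliminary analyses to assess for the efficacy of D-cycloserine". The stated purpose is efficacy, not safety. The note is permissive and says nothing more about the looks.

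Section 4 (Subject Enrollment) and the Overview in Section 5 carry the same blinding rule: "None of the investigators will be privy to the code, except for the study physician in case of an emergency". Both have the research pharmacy create and hold the randomization schedule.

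Other relevant text:

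- Section 2 sets 25 treated patients per arm, hypothesises a significant advantage for DCS, and calls the study a source of pilot data: "We intend to conduct the proposed study to collect sufficient pilot data to apply for an externally funded larger-scale research project".
- Section 6 gives one significance level, p < .05, in a power statement for a single comparison of 25 against 25 (80% power at d = 0.78). It adds: "Moreover, we will estimate between-group effect sizes of this pilot study to be used in designing future studies".
- Section 5 (Psychological Assessments) describes the primary outcome, the BDD-YBOCS, as follows: "This reliable and valid 12-item semi-structured clinician-administered scale". Ratings continue to 1 and 6 months after treatment.
- Section 9 makes the PI, with the study physicians, responsible for deciding whether the research is altered or stopped. It gives no efficacy criterion and names no independent committee.

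**The concern.** There are two problems.

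**The blind.** An efficacy look is not an emergency, so the permission in Section 6 falls outside the only exception in Sections 4 and 5. The plan does not say who receives the code, or whether raters, therapists and the PI stay blind after a look. If a look is taken once ten subjects have post-treatment data, some 1- and 6-month ratings for those subjects may still be due. They could then be made by clinicians who know the allocation. The text permits this risk; it does not prescribe it.

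**The error rate.** Repeated testing at an unadjusted .05 raises the chance of a false positive if any significant look can be acted on or claimed. No boundary or alpha split is given. No passage provides for stopping on efficacy, and none excludes it. Stopping at a significant look would also inflate the effect size, which is the quantity the pilot is meant to pass on to later designs.

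**Working it through.** **1. The plan's own power figure.** Inputs from Section 6: 25 per arm, d = 0.78, p < .05. The plan does not state sidedness. The two-sided normal approximation gives

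Φ(0.78 × √(25/2) − 1.960) = Φ(2.758 − 1.960) = Φ(0.798) = 78.7%.

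The two-sided noncentral t (48 df) gives 77.1%. One-sided versions give 86–87%. The stated 80% therefore fits a two-sided test with a single analysis, and two-sided .05 is assumed below.

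**2. Looks allowed.** 50 / 10 = 5 analyses: four interim and one final, with 5, 10, 15, 20 and 25 per arm if the arms are equal at each look (assumed).

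**3. Type I error.** Trials were simulated under no effect with normal outcomes. At each look with n per arm, t = (difference in means) / (s√(2/n)) was compared with the two-sided .05 critical value on 2n − 2 df. A trial counts as an error if any analysis taken is significant.

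| Analyses taken (total subjects) | Type I error |
|---|---|
| 50 only | 5.0% |
| 40, 50 | 7.1% |
| 30, 50 | 8.0% |
| 20, 50 | 8.7% |
| 10, 50 | 9.3% |
| 20, 40, 50 | 10.2% |
| 20, 30, 40, 50 | 11.5% |
| 10, 20, 30, 40, 50 | 14.5% |

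The table uses 400,000 trials. Repeat runs agree within about 0.1 percentage point. With ANCOVA and an assumed pre–post correlation of 0.3 to 0.7, five analyses give 14.8–15.0%. With balance required only at 50 subjects (correlation 0.5), the figure is 14.9%. Over all five analyses, first-significant errors favouring DCS occur in 7.3% of null trials, against 2.5% for one test. In 9.6% of null trials some interim look is significant but the final analysis is not.

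**4. What the first look can show.** With 5 per arm, significance needs an observed d of at least t(.975, 8 df) × √(2/5) = 2.306 × 0.632 = 1.46. Power at d = 0.78 is 19%.

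**5. Effect on the estimate.** Suppose the trial stops at the first significant look, which is a rule the plan neither contains nor excludes. The true effect is unknown, so a range is shown (200,000 trials each):

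| True d | Stops before 50 | Mean estimated d: stopping / single analysis | Among significant trials: stopping / single |
|---|---|---|---|
| 0.20 | 18% | 0.28 / 0.20 | 0.82 / 0.67 |
| 0.50 | 43% | 0.70 / 0.51 | 1.08 / 0.79 |
| 0.78 | 74% | 1.06 / 0.79 | 1.20 / 0.91 |

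Across this range the mean estimate exceeds the single-analysis estimate by about 33–38%.

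**6. Cost of controlled looks.** O'Brien-Fleming bounds for five equally spaced analyses use nominal p = 2[1 − Φ(2.040 / √(k/5))] for k = 1 to 5. This gives .000005, .0013, .0084, .0226 and .041. Applied to t-tests, type I error is 5.1%. Power at d = 0.78 is 76%, against 77% for one final test.

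**The case against.** The strongest reply is that the inflation depends on a decision rule the plan does not contain. The note says the blind may be broken and calls the analyses preliminary. Section 6 then defines separate main analyses for the primary hypothesis. If claims rest on those alone and no look changes conduct, the final test keeps its 5% level. The study is also described as a pilot. This part stands: the 7–15% is conditional. It does not settle the matter, because the plan never says the looks are descriptive, and it states a significance hypothesis tested at p < .05.

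The range is one of scenarios, not bounds. Section 6 names both ANOVA and ANCOVA at two time points, and counting any of these at each look would push the upper figure above 15%.

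On blinding, Sections 4 and 5 are a standing rule, and the looks could be reconciled with it if a non-investigator ran them in confidence. The plan does not provide for that. It also does not define what ten subjects must have completed. If follow-up must be complete, no ratings remain for those subjects. If a look comes earlier, some do.

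Finally, Section 9's power to alter or stop sits among safety provisions and does not establish stopping for efficacy. It does give the decision to people the plan does not shield from interim results.

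**Conclusion.** The concern holds. The contradiction between Section 6 and Sections 4 and 5 is on the face of the text and depends on no assumption. The looks are an uncontrolled option: their number, test, threshold, recipients and consequences could all be chosen after seeing unblinded data.

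The size of the error inflation is conditional. It assumes that significance at any look counts, two-sided .05, near-equal arms and one test per look. Under those conditions type I error is 7.1% at the least (one look, at 40) and 14.5–15% with all four looks, against 5%. If the trial also stopped at first significance, the mean effect estimate would be about a third too large or slightly more. Because the sentence bears on both the blind and the primary test, it needs to be corrected, even in a pilot.

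**What to change.** Delete the sentence in Section 6. State that there will be one efficacy analysis, at two-sided .05, after the last post-treatment assessment. Someone with no part in rating or therapy should run it, and raters and therapists should stay blind until the 6-month follow-up is complete.

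If looks are wanted, the plan should:

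- fix their number and timing in advance, and say what ten subjects must have completed;
- name one test per look;
- have the research pharmacy release codes only to a statistician with no therapy, rating or management role;
- use the O'Brien-Fleming bounds above, recomputed if fewer than five analyses are planned.

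In either case, reconcile the wording with the blinding rule in Sections 4 and 5. Declaring the looks descriptive, with no stop or claim attached, would settle the error rate but not the unblinding. The documents do not say whether a look has already been taken; if one has, the plan should record it.

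The cost is protocol wording and the loss of informal early looks. Keeping five controlled analyses costs about one percentage point of power at d = 0.78 (77% to 76%).
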